Skin Sensitivity to light													
Skin soreness													
Skin redness													
Skin darkening													
Numbness													
Tingling													
Dizziness													
General Pain													
Headache													

*A=Absent, Con=Conservative therapy such as cold pack and lotion, M= Mild, Mod=Moderate, Med= Medication such as topical steroid, N= No, P= Present, R: Resolved, S: Severe, Stim= Stimulation, Y=Yes.

Figure 8. Shows the technician-filled tolerability form. The selected items are based on the most common reported adverse effects associated with tDCS.

D.6. Study Visits and Data Acquisition

D.6.1 Schedule of Events

	Baseline	End of each 20-min stimulation cycle*			Before/After ET	2-hr	24-hr	Day 4	Day 30	Day 90
		1(Bridging)	2 (adjunctive)	3 (adjunctive)						
Consent	✓									
History / Exam	✓									
Routine Labs	✓									
Vital Signs	✓	✓	✓	✓	✓					
Tolerability form/Skin Inspection*	✓	✓	✓	✓						
Multimodal MRI/CT	✓					✓	✓			
NIHSS	✓	✓	✓	✓	✓	✓	✓			✓
Modified Rankin Scale (mRS)	✓							✓	✓	✓
Barthel Index (BI)										✓
EuroQol (EQ-5D)										✓
AMC Linear Disability Scale										✓
Interval serious adverse events		✓	✓	✓	✓	✓	✓	✓	✓	✓
Concomitant/Interval medications/procedures	✓	✓	✓	✓	✓	✓	✓	✓	✓	✓

* Skin Inspection will be performed before each stimulation period

D.6.2. Baseline Evaluation

- Demographics (age, sex, race)
- Last known well time
- Past medical/surgical history including vascular diagnoses and risk factors (stroke, TIA, carotid stenosis, myocardial infarction, atrial fibrillation, peripheral arterial disease, hypertension, diabetes, dyslipidemia)
- Medications, including antithrombotics, antihypertensives, statins, anti-arrhythmics Family history of vascular disease;
- Tobacco (including timing, duration, amount), alcohol, and illicit drug use;
- Vital signs (systolic blood pressure, diastolic blood pressure, pulse, respiratory rate, oxygen saturation);
- Premorbid global disability (modified Rankin Scale);
- Neurological deficits severity (NIHSS);
- Laboratory results (CBC, platelet count, glucose, lytes, INR, PTT, LFTs).

D.6.3. C-tDCS Treatment

- Skin inspection before each cycle of stimulation
- Tolerability/AE Form – after each cycle of stimulation
- NIH Stroke Scale (NIHSS) after each cycle of stimulation

D.6.4. Endovascular thrombectomy (EVT)

- Records of all the time metrics related to EVT: time of decision to take to catheter angiography suite for EVT, time of arrival at the catheter angiography suite, time of Groin Puncture, the time that C-tDCS was aborted prior to EVT, door to puncture time, on clot time, time first device deployed, time of first device passed (the times for each pass and deployment will be recorded), Total duration of EVT.
- Type of device uses (stent-retriever vs aspiration catheter)
- Total number of device passes
- NIHSS before and after EVT
- Interval serious adverse events during EVT
- Interval medications/procedures during EVT

D.6.4. Early (2 Hours) After EVT

- NIHSS,
- Multimodal MRI/CT
- Interval serious adverse events
- Interval medications/procedures

D.6.5. Late (24 Hours) After EVT

- NIHSS
- Multimodal MRI/CT
- Interval serious adverse events
- Interval medications/procedures

D.6.6. Day 4

- Modified Rankin Scale (mRS)
- Interval serious adverse events
- Interval medications/procedures

D.6.7. Day 30

- mRS (phone),
- Interval serious adverse events
- Interval medications/procedures

D.6.8. Day 90

- NIHSS,
- Modified Rankin Scale (mRS)
- AMC Linear Disability Scale (granular disability)
- Barthel Index (BI) (activities of daily living)
- EuroQol (EQ-5D) (health-related quality of life)
- Interval serious adverse events
- Interval medications/procedures

D.6.9. Imaging Assessments

- Baseline

Emergent multimodal MR and CT is currently acquired as the routine initial imaging study in all acute stroke patients at UCLA. In patients receiving MRI, a 1.5 T or 3 T scanner equipped with echo-planar imaging capability is used for rapid acquisition of diffusion and perfusion scans. The standard clinical MRI protocol includes Gradient Recall- Echo (GRE), DWI, FLAIR (Fluid-Attenuated Recovery Image), PWI and MR angiography. The ADC (apparent -diffusion coefficient) values derived from DWI acquisition ($b=0, 1000 \text{ s/mm}^2$ applied in each of three principal gradient directions) will be used to delineate the volume of ischemic core. The tissue with ADC values of $\leq 620 \mu\text{m}^2/\text{s}$ will be considered ischemic core, indicative of tissue with advanced, irreversible bioenergetic compromise. FLAIR delineates early parenchymal signal abnormality associated with ischemia and slow retrograde flow in leptomeningeal collaterals appearing as FLAIR vascular hyperintensity (FVH). The GRE sequence is used to evaluate the presence of intracranial hemorrhage and deoxygenated leptomeningeal collaterals appearing as GRE vascular hypointensity (GVH). PWI is acquired with sequential T2*-weighted (gradient echo) EPI time sequence scanning. Early in the time series, a bolus (0.1 mmol/kg) of MRI contrast material is rapidly infused (5 ml/sec through an 18 or larger gauge angiocatheter) using a power injector. The perfusion lesion volume (tissue at risk volume) will be the region with $\text{Tmax} \geq 6\text{sec}$ ($\text{Tmax} = \text{the time delay from}$

the arrival of contrast to its peak concentration at the tissue vasculature). ^{43,44} Intracranial CEMRA (Contrast-Enhanced MRA) will identify large vessel occlusion.

In patients receiving CT, the standard clinical CT protocol includes non-contrast CT (NCCT), multiphase CT angiography, CT perfusion (CTP) processed through RAPID software. NCCT is used to rule out acute intracranial hemorrhage appearing as hyperdensity. The tissue with rCBF < 30% on CTP will be considered ischemic core and the perfusion lesion volume (tissue at risk volume) will be the region with Tmax ≥ 6sec. CT angiography (CTA) will identify large vessel occlusion.

- Endovascular Thrombectomy

Patients will be undergoing cerebral angiography as part of the endovascular thrombectomy for treatment of acute ischemic stroke due to large vessel occlusion. The following data from pre-reperfusion cerebral angiography images will be collected: Target vessel occlusion for mechanical thrombectomy procedure, collateral grade prior to EVT (measured with the ASITN collateral grading scale). The following data will be collected from the post-reperfusion cerebral angiography images: arterial occlusion lesion: 1) Reperfusion, as measured with the expanded thrombolysis In cerebral infarction scale (eTICI) after final device pass (TICI 0, TICI 1, TICI 2a, TICI 2b, TICI 2c, TICI3); and 2) Recanalization, as measured with the arterial occlusive lesion (AOL) scale (0-No reduction of target thrombus, 1 – Reduced thrombus size but no recanalization, 2 – Partial recanalization, 3 – Complete recanalization).

TICI scale will be defined as the following: 0 – No perfusion, 1 – Antegrade reperfusion past the initial occlusion, but limited distal branch filling with little or slow distal reperfusion, 2a – Antegrade reperfusion of less than half of the occluded target artery previously ischemic territory (eg, in 1 major division of the MCA and its territory), 2b – Antegrade reperfusion of 51-90% of the previously occluded target artery ischemic territory, 2c – Anterograde perfusion of >90% but less than TICI 3 (i.e. near complete reperfusion), 3 – Complete antegrade reperfusion of the previously occluded target artery ischemic territory, with absence of visualized occlusion in all distal branches.⁴⁵

- 2h and 24h Post- Endovascular Thrombectomy

Follow-up MR/CT multimodal imaging will be obtained routinely at UCLA at 2h and 24h post-thrombectomy (supported by Radiology Dept. research funds). MRI Imaging sequences will include DWI/FLAIR/GRE/PWI/CEMRA and CT imaging sequences will consist of NCCT/CTA/CTP. RAPID image processing software will be applied to the above images to quantify, at the baseline, 2h, and 24h time-points: 1) Early penumbra preservation: Volume of baseline penumbra tissue not progressing to ischemic core at 2h; 2) Penumbra salvage: Volume of baseline penumbra tissue not progressing to ischemic core at 24h; 3) Early collateral flow enhancement: Perfusion lesion volume at baseline – Perfusion lesion volume at 2h; 4) Sustained collateral flow enhancement: Perfusion lesion volume at baseline – Perfusion lesion volume at 24h; 5) Early infarct growth: Ischemic core lesion volume at 2h – Ischemic core lesion volume at baseline; and 6) Final infarct growth: Ischemic core lesion volume at 24h – Ischemic core lesion volume at baseline. Additional location and extent of ischemic injury at baseline, 2h, and 24h will be rated using the ASPECTS scoring system.

D.6.10. Adverse Events

D.6.10.1 Serious Adverse Events (SAEs)

All serious adverse events occurring during the 90 days of study participation will be recorded. A serious adverse event is any adverse event that is fatal, is life-threatening, is permanently or substantially disabling, requires or prolongs hospitalization, or requires medical or surgical intervention to prevent one of the above outcomes.¹⁸

D.6.10.2 Symptomatic intracranial hemorrhage

The lead safety endpoint adverse event is symptomatic intracranial hemorrhage (SICH), defined using the SWIFT PRIME trial criteria ⁴⁶: an increase of 4 or more points on the NIHSS within 24 hours of stimulation associated with parenchymal hematoma type 1 (PH1), parenchymal hematoma type 2 (PH2), remote intraparenchymal hemorrhage (RIH), subarachnoid hemorrhage (SAH), or intraventricular hemorrhage (IVH). In addition, all hemorrhages, both symptomatic and asymptomatic, will also be separately classified and analyzed by radiologic subtype, as hemorrhagic infarction type 1 (HI1), hemorrhagic infarction type 2 (HI2), PH1, PH2, RIH, SAH, or IVH.⁴⁶ A central neuroimaging core lab, blinded to treatment assignment, will review all brain scans obtained at 24h and rate presence and type of radiologic hemorrhagic transformation. In addition, in patients who experienced worsening by 4 or more NIHSS points in the first 24 hours, they will review any and all additional brain MRI or CT scans obtained during the 24h time period,

SICH is the primary safety endpoint of the current trial, but trial results will be assessed on a variety of additional safety, feasibility, and tolerability results as well. It is anticipated that, after completion of the current trial, the judgement of whether to proceed directly to a pivotal trial, to proceed to a larger safety and preliminary efficacy trial, or to not proceed with further development, will rest on a considered and informed assessment of all outcome measures. It is important, therefore, to collect data on a wide range of safety endpoints and a wide range of measures of functional outcome, as is planned in this proposal. In making the selection of a primary safety endpoint, an emphasis was placed on ensuring patient safety throughout the course of the trial by choosing an endpoint with uncontested clinical relevance (Symptomatic Intracranial Hemorrhage).

D.6.10.3 Additional Adverse Events with Specific Interrogation

In addition to general screening for all serious adverse events and focused elicitation of symptomatic intracranial hemorrhage events, the following events will be specifically interrogated for and recorded in the case report forms: skin redness, scalp rash, hair loss, seizure, headache, sensitivity to light, new ischemic stroke, deep venous thrombosis, pulmonary embolism, pneumonia, acute MI.

E. Safety Monitoring

E.1. Data and Safety Monitoring Plan

The trial will be monitored by an Independent Data and Safety Monitoring Board (DSMB). [name] from department of neurorehabilitation will lead the DSMB. DSMB will assess for the causal relationship of the serious adverse event to the study treatment as definite, probable, possible, unlikely, or unrelated.

DSMB will meet at the completion of each dose tier, review all safety data, and determine whether the study will proceed to the next dose tier. DSMB deliberations will be guided by: 1) a formal stopping/escalation rule, based on the occurrence of the lead safety endpoint, symptomatic intracranial hemorrhage (SICH), and 2) The DSMB members' clinical judgement upon review of all other safety outcomes. In addition, the Food and Drug Administration (FDA) will be notified if there is one occurrence of SICH prior to repeating the tier or escalating to a higher tier. The DSMB, along with the investigators, will also continuously monitor door-to-puncture and imaging-to-puncture times in enrolled patients, comparing them with national guidelines from American Heart/American Stroke Association (AHA/ASA), the Society of Neurointerventional Surgery (SNIS), the Society of Vascular and Interventional Neurology (SVIN) and academic medical center comparator hospitals to ensure that start of thrombectomy is not being delayed by study procedures.

E. 2. Statistical Design and Analyses Plan

E.2.1. Sample size

The study sample size derives from the use of the 3+3, rule-based, modified Fibonacci, dose escalation design, with 3:1 randomization to active treatment vs sham control. There will be 6 dose tiers, reflecting increasing intensity and duration of stimulation (Figure 7). The 3+3 study design (3 patients and 1 sham) with 6 dose tiers yields a sample size of at least 24 and potentially up to 48. The 3+3 design is the classical approach to dose escalation in first-in-human studies.^{47,48} While newer, adaptive designs for dose escalation trials have been developed, they are more complex and have limited advantages when major toxicities are not expected.⁴⁹ Therefore, the rule-based, 3+3 design remains the dominantly employed approach in current dose-escalation studies. We will take every step to avoid missing data by scheduling of the follow-up visits early in visit time windows and readiness to travel to the patient's location to perform needed assessments. Should any missing data occur, primary analyses will be performed using multiple imputation, with sensitivity analyses including complete case and worst possible outcome analyses.⁵⁰

E.2.2. Baseline characteristics

The demographic and baseline clinical characteristics of the study population will be delineated with standard descriptive statistics. Categorical variables describing the clinical history, examination findings, and initial treatment will be summarized by frequencies. Continuous variables such as vital signs, laboratory results, and time variables will be characterized by means, standard deviations, and 95% confidence intervals (CI). Ordinal and non-normally distributed variables (such as the NIHSS) will be characterized by medians and interquartile ranges. Baseline characteristics will be compared between the tDCS stimulation group with sham group to assess covariate balance. Wilcoxon Rank-Sum tests will be used for continuous or ordinal variables; Fisher's exact tests and chi-square tests will be used for grouped or nominal categorical variables.

E.2.3. Safety and Tolerability (Specific Aim 1)

E.2.3.1 Dose Escalation

The study Data and Safety Monitoring Board (DSMB) will meet at the completion of each dose tier, review all safety data, and determine whether the study will proceed to the next dose tier. DSMB deliberations will be

guided by: 1) a formal stopping/escalation rule, based on the occurrence of the lead safety endpoint, symptomatic intracranial hemorrhage (SICH), and 2) The DSMB members' clinical judgement upon review of all other safety outcomes. The formal dose escalation rule uses SICH frequency to gate the occurrence and pace of escalation through the 6 dose tiers. If no SICH occurs in the 3 active patients at a dose tier, enrollment may escalate to the next dose tier. If one SICH occurs, 3 more active (and 1 more control) patient will be enrolled at that dose tier before escalation. If 2 SICHs occur at a dose tier, further study enrollment is held until detailed review by the DSMB (Fig 6). In addition, whenever the formal SICH criteria for dose escalation has been met, the DSMB will formally meet, review the SICH data and all other safety data, and advice regarding proceeding to the next tier, continuing at the current tier, or placing the study on hold.

E.2.3.2. Primary Safety Endpoint Analysis

For the final statistical analysis of the primary SICH safety endpoint, a chi-square test will be used to detect differences in the rate of SICH between the active treatment and sham patients and higher and lower dose tiers. The treatment will be considered to have exhibited adequate safety in the current trial to proceed to future, larger, pivotal efficacy trials if tDCS results in lower or equivalent rates of SICH compared to sham.

E.2.3.3. Secondary Safety Endpoints Analysis

In secondary safety endpoint analyses, the following will be compared between the active treatment and sham patients, and between higher and lower dose tiers, using chi-squared tests: **1)** Asymptomatic ICH by 24h (intracranial hemorrhage not associated with NIHSS worsening ≥ 4); **2)** Early neurologic deterioration (worsening ≥ 4 on NIHSS during the 24-hour period after stimulation, with or without intracranial hemorrhage); **3)** All-cause mortality at day 90 (mRS); and **4)** All serious adverse events.

E.3.3. Tolerability Endpoint Analysis

The lead tolerability endpoint is completion of the protocol-assigned stimulation treatment without early cessation due to cutaneous, neurologic, nociceptive or other adverse effects. Experience with tDCS in post-stroke patients indicates only infrequent cutaneous (itching, tingling) adverse effects are likely to occur. Accordingly, for the current study, a patient will be considered to have tolerated the procedure if at least 75% of the stimulus period was completed. The treatment will be considered generally tolerable if, among all enrolled patients, tolerated procedures are achieved in $\geq 90\%$ of patients, assessed with a one-sided p value of 0.025. Secondary tolerability endpoints will be the rate and severity of cutaneous, neurological, and pain items of the technician-filled (Figure 7), descriptively compared between active treatment and sham patients, and between higher and lower dose tiers.

E.3.4. Feasibility Endpoint Analysis (Specific Aim 2)

A time-motion analysis and mock run-throughs will be conducted prior to first enrollment. Nonetheless, it is anticipated that processes to optimize rapid placement of the cap and electrodes will continue to improve with experience gained from initially enrolled patients. The predefined success threshold for feasibility will be median times from randomization to bridging C-tDCS initiation and the time from end of EVT procedure to adjunctive C-tDCS initiation ≤ 10 minutes in the last 4 and 10 enrolled patients, respectively.

E.3.5. Exploratory Efficacy Endpoints Analysis (Specific Aim 3)

E.3.5.1. Exploratory Clinical Efficacy Endpoints

This study is underpowered to definitively determine efficacy, so all clinical efficacy analyses will be purely exploratory and descriptive. Four clinical outcome measures were selected based on their reliability, familiarity to the neurologic community, and adaptability for use in patients who have had a stroke. These endpoints are: the modified Rankin Scale (mRS), a rating of global disability; the Barthel Index (BI), a measure of instrumental activities of daily living; the National Institutes of Health Stroke Scale (NIHSS), a measure of neurologic deficit severity; and the EuroQol (EQ-5D), an assessment of health-related quality of life; and AMC Linear Disability Scale, a granular degree of disability.

Clinical efficacy endpoints will be characterized in the active and sham patients, and in higher and lower dose tiers. Early course clinical efficacy endpoints of greatest interest that will be explored are: **1)** Normalized change in neurologic deficit from baseline to 24h (normalized delta NIHSS – linear variable, analyzed with means and 95% CIs; and **2)** Degree of neurologic deficit at 24h (NIHSS – quasi-linear variable, analyzed with means and 95% CIs). Final outcome clinical efficacy endpoints of greatest interest that will be explored are: **1)** Degree of disability at 90 days, assessed across all 7 levels of the modified Rankin Scale – ordinal variable, analyzed with medians (IQRs) and means (95% CIs); **2)** Functional independence (mRS 0-2) at 90 days – binary variable, analyzed with rates and 95% CIs; **3)** Granular degree of disability at 90 days (AMC Linear Disability Scale) –

linear variable, analyzed with means and 95% CIs; and **4) Health-related quality of life (EQ-5D)** – linear variable, analyzed with means and 95% CIs.

E.3.5.2. Exploratory Imaging Biomarker Efficacy Endpoints

This study is underpowered to definitively determine efficacy, so all imaging efficacy analyses will be purely exploratory and descriptive. The imaging efficacy analysis will be done on the subgroup of patients (including tier 5 and 6 patients who have presence of salvageable penumbra in their entry criteria) with baseline pre-EVT penumbral imaging demonstrating presence of salvageable penumbra with $T_{max} > 6$ sec/ ischemic core volume of ≥ 1.2 .

Imaging biomarker efficacy endpoints will be characterized in the active and sham patients, and in higher and lower dose tiers, using means and 95% confidence intervals. The six imaging efficacy endpoints of greatest interest that will be explored are: early and late penumbral salvage, early and late collateral flow enhancement, and early and late infarct growth.

References:

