We will implement a traditional 3+3 (rule-based, modified Fibonacci) dose escalation design, with 3:1 randomization to active treatment vs sham control. There will be 6 dose tiers, reflecting increasing intensity and duration of stimulation:

Tier 1 – 1 mA, single 20 - min cycle, will start at the conclusion of the EVT procedure in patients with less than a complete EVT recanalization (the thrombolysis in cerebral infarction (TICI) grading of <2c and 3) and negative immediate post-EVT CT scan for a definitive evidence of intracranial hemorrhage (ICH).

Tier 2 – 2 mA, single 20 min cycle, will start at the conclusion of the EVT procedure in patients with TICI<2c and 3 and negative immediate post-EVT CT scan for a definitive evidence of ICH.

Tier 3 – 1 mA, in 2 treatment cycles. First cycle will be a 20 min cycle, administered after the conclusion of the EVT procedure in patients with TICI<2c and 3 and negative immediate post-EVT CT scan for a definitive evidence of ICH. The second cycle will start 20 minutes after the end of the first cycle, and will last 20 minutes.

Tier 4 – 2 mA, in 2 treatment cycles. First cycle will be a 20 min cycle, administered after the conclusion of the EVT procedure in patients with TICI<2c and 3 and negative immediate post-EVT CT scan for a definitive evidence of ICH. The second cycle will start 20 minutes after the end of the first cycle, and will last 20 minutes.

Tier 5 - 1 mA, in 3 treatment cycles. First cycle will be a 20 min cycle, administered after initial imaging either in the Roland Reagan Medical Center or mobile stroke unit and prior to arterial puncture (cycle will be shorter than 20 minutes if EVT puncture is ready to proceed, in order not to delay EVT). The second cycle will start at the conclusion of the EVT procedure in patients with TICI<2c and 3 and negative immediate post-EVT CT scan for a definitive evidence of ICH (and not sooner than 20 minutes after the end of the first cycle), and will last 20 minutes. The third cycle will start 20 minutes after the end of the second cycle, and will last 20 minutes.

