Tier 6 - 2 mA, in 3 treatment cycles. First cycle will be a 20 min cycle, administered after initial imaging either in the Roland Reagan Medical Center or mobile stroke unit and prior to arterial puncture (cycle will be shorter than 20 minutes if EVT puncture is ready to proceed, in order not to delay EVT). The second cycle will start at the conclusion of the EVT procedure in patients with TICI<2c and 3 and negative immediate post-EVT CT scan for a definitive evidence of ICH (and not sooner than 20 minutes after the end of the first cycle), and will last 20 minutes. The third cycle will start 20 minutes after the end of the second cycle, and will last 20 minutes.

Patients in the sham stimulation arm at all the tiers will have the cap and electrodes in place, but without any delivered electrical stimulation. While the highest dose tier in this study is expected to be fully safe, based on preclinical and clinical studies ^{11,18}, since this is a first-in-human study in acute stroke, a formal escalation to higher dose tiers is prudent.

[figure not shown]

Figure 7. This figure shows the 6 escalating tiers. Blue represents 1 mA, purple shows 2 mA of C-tDCS. The black/white neuroangi suite icon represents the endovascular thrombectomy (EVT) procedure, occurring before the adjunctive C-tDCS at all tiers if EVT results in a less than a complete recanalization (TICI <2c, 3). At tiers 5 and 6, bridging C-tDCS occurs for up to 20' before EVT. Symptomatic ICH (SICH) in none of the three C-tDCS patients in a tier will result in escalation. However, if SICH occurs in one C-tDCS patient, 3 more C-tDCS patients and 1 more sham will be enrolled at the same tier.

D.4. Management pre, during, and post adjunctive stimulation period

As soon as the endovascular thrombectomy (EVT) ends, a CT head will be obtained in patients with less than a complete EVT reperfusion (TICI < 2c,3) and if negative for definitive evidence of intracranial hemorrhage, then the patient will be randomized, and the adjunct stimulation will be initiated in neurosurgical intensive care unit according to the tier that patient is assigned to.

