After randomization and during the stimulation, all patients will be monitored closely by a physician-investigator. NIHSS will be obtained at the end of each 20-minute stimulation cycle and a visual inspection of the skin and rate degree of any potential erythema under the electrode will be performed. Then, a tolerability form will be completed based on validated cutaneous, neurological, and pain items of the PRO-CTAE (Patient-Reported Outcomes version of the Common Terminology Criteria for Adverse Events) (Figure 8).^{40,41}

After the stimulation, nursing neurologic assessments will be performed by Neurointensive Care Unit with extensive experience in monitoring acute stroke patients. Specifically, patients will be monitored for any signs of neurological worsening and will be queried on development of new or worsening neurological symptoms, including headache, dizziness, numbness, or weakness, etc. If any sign or symptom of neurological worsening is suspected, the patient will be immediately assessed by the on-call neurologist and an immediate brain imaging (CT or MRI) will be obtained. Neuro-checks will be performed at 1h and 2h after stimulation and then every 2 hours. Subsequent care will be continued in these settings, including medical management per national guidelines for acute ischemic stroke management issued by the American Stroke Association.⁴² Patients will not receive NSAIDs as concomitant therapy for the first 7 days after enrollment. All patients will undergo a multimodal MRI or CT including standard parenchymal images, non-invasive angiography, and perfusion studies and formal NIHSS assessment at 2-hour and 24-hour following the end of the stimulation tier as part of the study protocol.

D.5. Management pre, during, and post bridging stimulation

At tiers 5 and 6, hospital arriving patients who are candidates for EVT with an LVO detected on CT angiography and are being transferred to agio suite for EVT procedure will receive up-to-20 minutes of stimulation. See section D.4. for care during and post-stimulation.

Figure7: Technician-filled tolerability form	Presence		Severity		Effect on the study treatment (Shortened the stim duration)		Duration/Frequency			Treatment			
	A	P	M	Mod	S	Y	N	< 50 % of stim period	≥50% of stim period	lasted after stim period (min)	None	Con	Med
Adverse Events													
Rash													
Skin dryness													
Hair loss													
Itching													
Hives													

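### No skin check or tolerability form is scheduled after the last stimulation cycle, and the number of forms rises with tier, so late skin effects may be missed and the tier comparison mixes dose with observation

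*Combined protocol and SAP*

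**What the plan says.** **Around stimulation.** Section D.4 on management around adjunctive stimulation says "NIHSS will be obtained at the end of each 20-minute stimulation cycle and a visual inspection of the skin", after which the tolerability form is filled in. D.5 applies the same care to the bridging cycle. D.6.3 lists "Tolerability/AE Form – after each cycle of stimulation". The footnote to D.6.1 adds "Skin Inspection will be performed before each stimulation period".

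**After stimulation.** In D.6.1 the row for the form and skin inspection is ticked at baseline and at the cycles only. The lists for 2 hours, 24 hours, Day 4, Day 30 and Day 90 (second D.6.4 to D.6.8) carry interval serious adverse events and interval medications or procedures. They have no skin item and no non-serious event item. D.4 does provide neuro-checks at 1 and 2 hours and every 2 hours thereafter, and questioning about symptoms such as headache, dizziness and numbness.

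**Undated promise.** D.6.10.3 says that "skin redness, scalp rash, hair loss, seizure, headache, sensitivity to light" and several medical events will be specifically asked about and entered in the case report forms. It names no visit.

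**The form.** It lists rash, hives, hair loss, skin darkening and redness among its items, and has a column headed "lasted after stim period (min".

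**Use.** Hypothesis I-c refers to the absence of major stimulation-related pain, discomfort and skin changes. E.3.3 compares the rate and severity of the form items descriptively, active against sham and higher against lower tiers.

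**The concern.** If staff follow the schedule as written, the last dated look at the scalp comes when the last cycle ends. Some listed items, such as hair loss, darkening or rash, may not be visible then. The persistence column asks for something that lies in the future at that moment. D.3.2 expects some patients to be stuporous or aphasic, so spontaneous reporting of itching or soreness cannot be relied on.

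Two uses of the data are exposed. The skin part of Hypothesis I-c would rest on findings that stop with the current. The comparison between tiers in E.3.3 would set patients examined once against patients examined two or three times, over a longer span. C.3 describes skin redness as mildly dose-dependent, so this comparison is one that readers will look at.

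**Working it through.** **1. Where each item is scheduled**

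| Item | Baseline | Around each cycle | 2 h, 24 h | Day 4, 30, 90 |
|---|---|---|---|---|
| Form and skin inspection (D.6.1, D.6.3) | yes | yes | no | no |
| Neurological symptom questions (D.4) | – | – | yes, within routine neuro-checks | not stated |
| D.6.10.3 items | no visit named | no visit named | no visit named | no visit named |
| Serious adverse events (D.6.1) | – | yes | yes | yes |

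Nothing in D.4 or E.3.3 says that answers to the neurological questions are entered on the form or used in the tolerability analysis.

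**2. Forms per patient.** One form per cycle:

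- Tiers 1-2: "Tier 2 – 2 mA, single 20 min cycle" (tier 1 is the same at 1 mA), so k = 1.
- Tiers 3-4: "Tier 4 – 2 mA, in 2 treatment cycles" (tier 3 likewise at 1 mA), so k = 2.
- Tiers 5-6: "Tier 6 - 2 mA, in 3 treatment cycles" (tier 5 likewise at 1 mA), so k = 3, but k = 1 if TICI 2c or 3 is reached, because only the bridging cycle is then given.

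Pre-cycle inspections also rise by one per cycle. They are not counted below.

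In tiers 3-4 the second cycle starts 20 minutes after the first ends and lasts 20 minutes. Skin exposed in cycle 1 is therefore seen again about 20 and 40 minutes after that cycle ended. In tiers 1-2 no later look is scheduled.

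**3. Active against sham.** The plan's sample size reproduces: 6 × (3 + 1) = 24 and 6 × 2 × (3 + 1) = 48. At the minimum of 24, with full cycles:

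- Active: 3 × (1 + 1 + 2 + 2 + 3 + 3) = 36 forms in 18 patients, mean 2.0.
- Sham: 1 × 12 = 12 forms in 6 patients, mean 2.0.

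The planned looks are equal.

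**4. Possible effect of unequal looks on tiers.** The documents give no event rate. Assume a chance p per look, the same in all tiers, with looks independent. Then P(ever reported) = 1 − (1 − p)^k.

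| p (assumed) | k = 1 | k = 2 | k = 3 | ratio, 3 looks to 1 |
|---|---|---|---|---|
| 0.02 | 2.0% | 4.0% | 5.9% | 2.94 |
| 0.05 | 5.0% | 9.8% | 14.3% | 2.85 |
| 0.10 | 10.0% | 19.0% | 27.1% | 2.71 |
| 0.20 | 20.0% | 36.0% | 48.8% | 2.44 |
| 0.30 | 30.0% | 51.0% | 65.7% | 2.19 |

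E.3.3 does not define higher and lower tiers. If the split is 1-3 against 4-6 (assumed) and p = 0.10:

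- Lower: (0.10 + 0.10 + 0.19)/3 = 13.0%.
- Higher: (0.19 + 0.271 + 0.271)/3 = 24.4%.

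If the looks are fully correlated, P = p for every k and the ratio is 1.

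**5. Time zero of the 2-hour and 24-hour contacts.** D.4 counts from the end of the stimulation tier. The visit lists (second D.6.4, D.6.5) and the imaging text in D.6.9 count from thrombectomy. Let d be the delay in minutes from end of thrombectomy to first adjunctive current. One adjunctive cycle ends at d + 20, and two end at d + 20 + 20 + 20 = d + 60. A contact 120 minutes after thrombectomy then falls 100 − d or 60 − d minutes after the last current, a difference of 40 minutes.

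**The case against.** The strongest reply is that the plan does look later. Headache, dizziness and numbness are all form items and are asked about for hours afterwards. D.6.10.3 commits to recording redness, rash and hair loss whether or not they are serious. Interval medications and procedures are collected to Day 90, so a treated skin reaction could surface there. The form is completed after the cycle, and nothing says it closes at that moment. Its persistence column, and an abbreviation for resolved in its legend, suggest that some follow-up was intended. All of this stands. A reader might infer that non-serious effects are looked for only until the last cycle ends, or go unrecorded unless serious. The documents do not support either reading. What they lack is a date and a place in the schedule for the skin items.

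The second reply is that each extra form follows an extra 20-minute exposure, so a higher cumulative rate is partly a real duration effect. That also stands. A reader might take the 10%, 19% and 27% figures as the expected bias, but they rest on an assumed rate and on independent looks. The pairs 1-2, 3-4 and 5-6 have equal planned looks, so the 1 mA against 2 mA contrast within a pair is not disturbed. Nor is active against sham within a tier.

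The third reply is that no formal decision depends on these items. They are secondary and descriptive, the lead tolerability endpoint is completion of 75% of the stimulation period, and the formal escalation rule uses symptomatic haemorrhage. This limits the weight of the point but does not remove it, since the skin wording of Hypothesis I-c remains.

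**Conclusion.** The point holds in a limited form. There is no dated skin inspection or tolerability form after the last cycle, and the D.6.10.3 questioning has no visit. Late or persistent non-serious skin effects may therefore be missed. How many is unknown, because the documents give no rate of delayed effects.

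Planned forms differ by tier (1, 2, and up to 3), so a per-patient ever-reported comparison of tiers cannot separate dose and exposure from amount of observation. The inflation from looks alone lies between nil (fully correlated looks) and about 2.2 to 2.9 times for tiers 5-6 against tiers 1-2 (independent looks, assumed 2% to 30% per look, all three cycles given). The upper figures are a bound under those assumptions and should not be read as an estimate. The point does not touch the lead tolerability endpoint, the escalation rule or the active-sham comparison within a tier. It should be corrected, but it does not put the trial's main conclusions at risk.

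**What to change.** 1. In D.6.1 and the visit lists (second D.6.4 to D.6.6), add the tolerability form, a scalp inspection and the D.6.10.3 items to the existing 2-hour, 24-hour and Day 4 contacts. Complete the persistence column there.
2. Reconcile D.4 with the visit lists and D.6.9, so that the 2-hour and 24-hour tolerability assessments are timed from the end of the last cycle in every tier. Without this, the added assessments would not be at common times. Record the actual elapsed time, particularly for tier 5-6 patients whose only cycle precedes thrombectomy.
3. In E.3.3, report form items per cycle and at these common post-stimulation times, define higher and lower tiers, and state whether the post-stimulation neurological questions enter the analysis.

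The cost is protocol and case report form wording and a few minutes at contacts that already take place. Recorded rates of skin effects may rise slightly.
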